5.2. General Methods

5.2.1. Analyses for Binary Endpoints

Landmark (cross-sectional) analyses of key binary endpoints will calculate and test for risk differences using the method of (Chan and Zhang 1999).² Covariates will not be included in the primary analyses. Risk differences and 90% confidence intervals will be presented.

For all key binary endpoints such as PASI75, PASI90 and PGA scores etc that are measured repeatedly over time, will be analyzed using generalized linear mixed effect model (GLMM) with treatment group (defined as factor variable), visit, treatment group by visit interaction and subjects as the random effect. An unstructured covariance matrix will be used to fit such model. In case, if the model fails to converge, a covariance structure such as compound symmetry or autoregressive model may be used. Bayesian information criterion (BIC) will be used to assess the goodness of fit of the models. The model with the smallest BIC will be selected for inference. P-values and inference for relative risks between treatments will be provided based on the link function of logit.

For all binary endpoints, a summary based on the mITT Observed Efficacy Set of the number of subjects in each category based on observed cases in each treatment arm at each time point will be produced and the response rate will also be plotted against time, by treatment group.

Exploratory categorical analyses that include or assess the effects of covariates may be done on an exploratory basis. Exploratory longitudinal analyses may also be performed including appropriate covariates of interest.

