6. ANALYSES AND SUMMARIES

Analysis will be done pairwise between each of the PF-06826647 treated groups and the placebo group. An analysis with point estimates of the difference, the associated 90% confidence intervals and p-values will also be reported.

A summary of analyses for clinical efficacy endpoints is provided in [Appendix 1](#). Visit windows to be used for all efficacy analyses and some relevant safety analyses are detailed in [Appendix 2.1](#).

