Appendix 4. SAS Code for Estimand 2 –Change from Baseline in PASI Score

```

libname C2501004 "/Volumes/app/..... /data_vai" ;

data adps;
set C2501004.adps;
if paramcd="PASI0246" and 2<avisitn<=9 and ANL01FL="Y" ;
keep subjid avisitn aval base trtan paramcd anl01fl;
run;

**example data for a single visit;
**created from systemic study ;
**ignore values, only used for illustration;

*Multiple Imputation;
**data already has one record per subject per visit even if;
**data is missing. Proc Mi needs missing values in order to impute;
data _data1;
set ADPS;
where avisitn=9;
run;

proc sort data=data1 out=data1 miss;
by trtan;
run;

*imputing aval=observed so range of endpoint 0-72 can be included in;
*mi procedure;
proc mi data=data1 _miss seed=2501004 nimpute=1000 out=outimp;
class trtan;
monotone regpmm(aval= base/details k=5);
mnar model( aval/modelobs = (trtan="1"));
var base aval;
run;
proc univariate data=outimp;
var aval;
histogram;
run;
data outimp1;
set outimp;
chg = aval - base;
**calculate chg from baseline;
pchg= ((AVAL - BASE)/BASE)*100;
**calculate pchg from baseline;
run;
proc sort data = outimp1 out = data1;

```

by imputation trtan usubjid;
run;

proc mixed data=data1 order=data;
 by imputation;
 class trtan;
 model CHG = trtan base;
 lsmeans trtan/ diff alpha=.1;
 ods output lsmeans=mmmr diff=dmrm(where=(trtan=1));
run;

**now use mianalyze on lsmean;
 **First sort by trtan;
proc sort data=mmrm out=lsout1;
 by trtan _imputation_;
run;
 **now mianalyze by trtan;
 **NB mianalyze only uses estimates and standard errors not CI limits etc.;

proc mianalyze data=lsout1 alpha=.1;
 **specify alpha for 90% CIs here;
 by trtan;
 modeleffects estimate;
 stderr stderr;
 ods output parameterestimates=lsmean;
run;

**now use mianalyze on lsmean differences;
 **First sort by trtan;
proc sort data=dmrm out=diffsout1;
 by trtan _imputation_;
run;
 **now mianalyze by trtan;
 **NB mianalyze only uses estimates and standard errors not CI limits etc.;

proc mianalyze data=diffsout1 alpha=.1;
 **specify alpha for 90% CIs here;
 by trtan;
 modeleffects estimate;
 stderr stderr;
 ods output parameterestimates=diff;
run;

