Appendix 5. SAS Code for the Generalized Linear Mixed Model for Binary Longitudinal Data

```
PROC GLIMMIX DATA =<DATA> METHOD=RMPL;  
  CLASS SUBJID TRTPN VISIT;  
  MODEL RESPONSE (EVENT = "1") = TRTPN VISIT TRTPN * VISIT / ALPHA = 0.1  
  DIST=BINARY LINK=LOGIT;  
  RANDOM VISIT /SUBJECT = SUBJID TYPE=UN RESIDUAL;  
  LSMEANS TRTPN * VISIT / ILINK COV DIFF CL;  
RUN;
```

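### The logit model behind the PASI 90 sensitivity analysis is promised to give relative risks, but its code forms none, does not set 90% on the contrasts, and has no rule for a Week 16 cell without responders

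*SAP*

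**What the plan says.** SAP 5.2.1 describes a generalized linear mixed model for binary endpoints measured repeatedly, with treatment, visit, their interaction and a subject random effect. On its output it says: "P-values and inference for relative risks between treatments will be provided based on the link function of logit". If the unstructured covariance fails to converge, "a covariance structure such as compound symmetry or autoregressive model may be used", and "The model with the smallest BIC will be selected for inference". SAP 6.1.1.2 and Appendix 1 make this model the sensitivity/supplementary analysis of PASI 90, on observed data, with missingness assumed completely at random or at random. SAP 6 adds, for each dose against placebo: "An analysis with point estimates of the difference, the associated 90% confidence intervals and p-values will also be reported". The population-level summary of the primary estimand (SAP 2.1.1) is a difference in proportions.

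Appendix 5 fits a logit-link model by METHOD=RMPL. Its MODEL statement carries "TRTPN VISIT TRTPN * VISIT / ALPHA = 0.1", its covariance line is "RANDOM VISIT /SUBJECT = SUBJID TYPE=UN RESIDUAL", and its output line is "LSMEANS TRTPN * VISIT / ILINK COV DIFF CL".

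**The concern.** Read against each other, the text and the code disagree on the effect measure, leave the interval level of the contrasts unset, and describe different models (a subject random effect in 5.2.1, a residual-side marginal covariance in Appendix 5). Nothing is said about a treatment-by-visit cell with no responders, although the protocol expects low PASI 90 rates on placebo and at the lowest dose.

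This is the planned model-based check of the primary result under missing at random. If these choices are left open, they will be made once the data are visible. An odds ratio read as the promised relative risk would greatly exaggerate the effect. With an empty placebo cell, every dose contrast from the model would be unusable.

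**Working it through.** The plan states no figure on this point, so the main check is text against code. The arithmetic below shows the size.

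**Inputs.** Placebo rate 5% and a 35-point effect, so 40% on active (Protocol 9.2). Projected Week 16 rates of 3%, 13%, 47% and 83% for 50, 100, 200 and 400 mg (Protocol 4.3). Arm sizes 40 or 20 randomised, 32 or 16 completers (Protocol 9.2). The sizes are coherent: 128/(1 − 0.20) = 160.

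**1. Effect measure.** With a logit link, DIFF gives differences in log odds, ILINK gives cell probabilities, and COV gives the covariance matrix on the logit scale. No statement forms a ratio or difference of probabilities. With RR = p1/p0, OR = [p1/(1−p1)]/[p0/(1−p0)] and placebo odds 0.05/0.95 = 0.0526:

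| Active rate | RR | OR |
|---|---|---|
| 40% | 0.40/0.05 = 8.0 | 0.6667/0.0526 = 12.7 |
| 47% | 0.47/0.05 = 9.4 | 0.8868/0.0526 = 16.8 |
| 83% | 0.83/0.05 = 16.6 | 4.8824/0.0526 = 92.8 |

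**2. Interval level.** Take 2/40 against 19/40 as an assumed outcome near 5% and 47%.

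- Log OR = 2.844, with SE = √(1/2 + 1/38 + 1/19 + 1/21) = 0.792. OR = 17.2, 90% CI 4.7 to 63.2, 95% CI 3.6 to 81.1.
- The promised RR is 9.5, with delta-method 90% CI 3.0 to 30.5.
- On the log scale a 95% interval is 1.960/1.645 = 1.19 times as wide as a 90% interval.

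**3. Chance of an empty Week 16 cell**, (1−p)^n:

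| Cell | Rate | All randomised | Completers |
|---|---|---|---|
| Placebo | 5% | 0.95^40 = 12.9% | 0.95^32 = 19.4% |
| 50 mg | 3% | 0.97^20 = 54.4% | 0.97^16 = 61.4% |
| 100 mg | 13% | 0.87^20 = 6.2% | 0.87^16 = 10.8% |

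If the true placebo rate is not 5%, the placebo figures (40, then 32 participants) are 45% and 52% at 2%, 30% and 38% at 3%, 4% and 7% at 8%, and 1.5% and 3% at 10%.

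**4. What an empty cell does.** In a two-cell logistic fit to 0/40 against 19/40, the estimate never settles:

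| Iterations | Log OR | SE | Wald p |
|---|---|---|---|
| 8 | 9.10 | 15.8 | 0.56 |
| 10 | 11.10 | 42.8 | 0.80 |
| 15 | 16.10 | 522 | 0.98 |
| 20 | 21.10 | 6355 | 0.997 |

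On the same counts the exact unconditional one-sided p is 1.4 × 10⁻⁷. The Chan-Zhang 90% interval for the 47.5-point difference is 33.8 to 61.6 points (computed in Python, not PROC BINOMIAL).

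**5. Whether another covariance structure helps.** The model has a free mean for each treatment-by-visit cell. A marginal logit model was fitted by estimating equations in Python, with three visits and an assumed time course.

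- With complete data and no empty cells, fitted means equalled observed proportions under independence, exchangeable and unstructured correlation.
- With a last-visit placebo cell of 0/40, the exchangeable fit gave a logit contrast above 25 and p above 0.999 in 30 of 30 trials.
- With 20% of last-visit values missing at random, 14 of 30 fits failed and the other 16 gave contrasts above 27.

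**The case against.** The strongest reply is that little depends on this. The study's decision rests on the exact Chan-Zhang comparison with Hochberg adjustment, which copes with an empty cell. Observed counts and rates are also reported, so a reader would still see 0/40. That stands, and it sets the importance.

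Other readings go further than the documents allow:

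- A reader might infer that the code cannot deliver a relative risk. It can be derived: the inverse-link probabilities and the COV matrix are what a delta-method interval needs. The step is simply not planned or coded. With non-empty cells the p-values are usable, because an odds ratio of 1 and a relative risk of 1 are the same null.
- A reader might infer that the SAP commits to 95% limits. SAP 6 requires 90%. That LSMEANS falls back to 95% when alpha is set only on MODEL is SAS behaviour, not SAP text. Appendix 4 does write "lsmeans trtan/ diff alpha=.1", but its reported limits come from the later MIANALYZE step, so the comparison is weak support.
- A reader might conclude that BIC selection is always invalid here. When fitted means agree across structures, so do the pseudo-data. The difficulty arises with missing data, which is the case this analysis is for.
- A reader might infer that scores after prohibited medication enter the model as observed. SAP 5.2.1 and 5.3 tie the Observed Efficacy Set to summaries. SAP 6.1.1.2 does not say which set the model uses.

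Finally, the illustrations are not the planned seven-visit model. PROC GLIMMIX was not run, so whether its non-convergence fallback would trigger is unknown.

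**Conclusion.** The concern holds as a minor defect confined to the sensitivity and supplementary analyses of binary endpoints. The promised effect measure has no code, the contrasts are not set to the required level, and an empty cell has no rule.

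The mismatch between text and code rests on the documents alone. The size of the empty-cell risk rests on the 5% planning rate and the projected 3% at 50 mg, and Protocol 4.3 itself calls the extrapolation to Week 16 uncertain. An empty placebo cell would affect all four dose comparisons; an empty 50 mg cell would affect only its own. That a zero cell has no finite logit contrast follows from the free cell means. The two-cell fit shows that the Wald p-value is then uninformative, but it does not show what GLIMMIX would print. The documents do not support any inference that the primary conclusion is at risk.

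**What to change.** 1. State one effect measure and code it with its 90% interval. The Week 16 risk difference from the inverse-link probabilities is preferable because it matches the primary scale; the promised relative risk by the delta method is the alternative. Label any exponentiated logit contrast an odds ratio.
2. Put ALPHA=0.1 on the LSMEANS statement in Appendix 5.
3. Add a zero-cell rule. If either cell has 0% or 100% responders, report no Wald logit contrast. Give the Chan-Zhang risk difference on the same observed data (Appendix 6 code), footnoted as an observed-case result and not one from the missing-at-random model.
4. Reword SAP 5.2.1 to describe the residual-side marginal model in Appendix 5. Replace BIC selection with a fixed order of covariance structures, because pseudo-likelihood BIC is not generally comparable across structures when data are missing.
5. Name the data set for the model. State how it handles data after prohibited medication, data after withdrawal of study drug (SAP 4.4) and data missing because of COVID-19 (SAP 4.5). These rules can differ from the primary analysis in several ways, so do not claim that only the missing-data assumption changes.

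The cost is SAP text and a few lines of code, with no new data. Under item 3 one contrast may come from a different method than its neighbours, hence the footnote.

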5.2.2. Analyses for Continuous Endpoints

Landmark (cross-sectional) analysis of key continuous endpoints will use analysis of covariance (ANCOVA). The ANCOVA model will include terms for treatment arm and baseline score of the dependent variable. Least-squares means at the mean overall baseline score will be presented along with 90% confidence intervals.

Mixed model repeated measures (MMRM) models will be used. The fixed effects of treatment, visit (Weeks 1, 2, 4, 6, 8, 12 and 16), and treatment-by-visit interaction will be included. Visit will be modeled as a categorical covariate. Unstructured covariance matrix will be assumed for the model errors. Compound symmetry covariance matrix will be used if the model with unstructured covariance doesn't converge.

When modeling the change from baseline values, the variable for visit will start with the first post-baseline visit, and the actual baseline value will be included as a covariate. At each visit, estimates of least square mean (LSM) values and the LSM differences between the PF-06826647 treated groups and placebo group will be derived from the model. The corresponding p-values and 90% confidence intervals will also be derived from the model.

Unless stated otherwise, descriptive summary statistics for all continuous variables will be presented on mITT Observed Efficacy Set by treatment group and will include the following: n, mean, median, standard deviation, minimum and maximum.

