6.2.3.1. Main analysis

- Estimand strategy: Secondary Estimand ([Section 2.1.2](#)) use a composite endpoint strategy. This estimand is intended to provide an estimate of the treatment effect in the absence of prohibited medication use in a population that may or may not be fully compliant with the treatment.

- Analysis set: mITT (Section 4.1) using data prepared in the description of the Secondary Estimand Continuous Endpoint Set.
- Analysis methodology: ANCOVA model with treatments arms and baseline score as dependent variable.
- Intercurrent events and missing data: These have been accounted for in the estimand (Section 2.1.2) and missing data will be imputed using a contro based imputation method (Section 5.3).
- Mean difference of change/percent change from baseline PASI score and 90% confidence intervals will be presented.

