6.2.3.2. Sensitivity/Supplementary Analysis

- Estimand strategy: Primarily this estimand is intended to provide an estimate of the treatment effect in the population level assuming missing data are either MCAS (Missing Completely at Random) or MAR (Missing at Random). Applicable statistics will be calculated at time points specified in the SoA.
- Population: mITT.
- Analysis methodology: MMRM and descriptive statistics.
- Missing Data: Observed Data.

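### The MMRM for change from baseline has one baseline slope for all visits; adding baseline-by-visit would recover precision for absolute PASI change at later visits (minor)

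*SAP*

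**What the plan says.** SAP 5.2.2 describes the MMRM for continuous endpoints: "The fixed effects of treatment, visit (Weeks 1, 2, 4, 6, 8, 12 and 16), and treatment-by-visit interaction will be included". For change from baseline it adds that "the actual baseline value will be included as a covariate". On the covariance it states "Unstructured covariance matrix will be assumed for the model errors", with compound symmetry as the fallback if that model does not converge. Least-squares mean differences are taken at each visit, and "The corresponding p-values and 90% confidence intervals will also be derived from the model".

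No section names a baseline-by-visit interaction, and the code appendices contain no MMRM program. The plain reading is therefore a single baseline main effect.

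The model has two uses for PASI:

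- **Week 16 change and percent change.** The MMRM is the sensitivity or supplementary analysis (SAP 6.2.3.2: "Analysis methodology: MMRM and descriptive statistics"). The main analysis in 6.2.3.1 is an ANCOVA after control-based imputation. That section's wording, "ANCOVA model with treatments arms and baseline score as dependent variable", is loose, but Appendix 4 settles it: the program keeps the Week 16 records and fits "model CHG = trtan base", so baseline is a covariate with its own Week 16 slope.
- **Other visits.** SAP 6.2.4 gives MMRM as the model for the continuous endpoints, including PASI, PP-NRS and PSI.

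**The concern.** PASI cannot fall below zero, so a participant's change is bounded by baseline: someone who clears fully changes by exactly minus the baseline score. If participants improve by a fraction *f* that does not depend on baseline, expected change is −*f* × baseline and the slope is −*f*. Early on, *f* is small. By Week 16 the protocol (section 4.3) projects PASI 90 rates of 47% and 83% at 200 mg and 400 mg, so the slope should by then be clearly negative.

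One slope cannot fit both ends. With an unstructured covariance, generalized least squares gives most weight to the visits with the smallest residual variance, which for change scores are the first ones. The fitted slope is then too shallow for Week 16. The unexplained baseline variation goes into the Week 16 residual and widens the interval for the contrast.

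At stake is the precision of the visit-wise PASI differences, p-values and 90% intervals. The sensitivity comparison at Week 16 also becomes less clean, because MMRM and ANCOVA would differ in baseline adjustment as well as in missing-data assumptions.

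**Working it through.** **Inputs from the documents.** Seven visits (SAP 5.2.2); 32/16/16/32/32 completers for placebo, 50, 100, 200 and 400 mg (protocol 9.2); baseline PASI of at least 12 (protocol 5.1). The plan states no standard error, SD or slope for PASI change, so it has no figure of its own to reproduce here.

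**Assumed.** Baseline PASI mean about 20 and SD 7 to 8, response curves, measurement noise, residual correlations, complete data.

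**Step 1: which slope is fitted.** Let β be the vector of visit-specific slopes and R the residual covariance given arm and baseline. The common slope is

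b = 1′R⁻¹β / 1′R⁻¹1.

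A two-visit illustration shows the weighting. Take residual SD 2 at Week 1 and 5 at Week 16 (a ratio of 40%).

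- Correlation 0.4: the covariance is 0.4 × 2 × 5 = 4, so R = [[4, 4], [4, 25]]. The weights are proportional to 25 − 4 = 21 for Week 1 and 4 − 4 = 0 for Week 16. The fitted slope is the Week 1 slope.
- Correlation 0.2: the covariance is 2, and the weights are 23 and 2, that is 0.92 and 0.08.

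**Step 2: cost at Week 16.** The misfit adds var(baseline) × (β₁₆ − b)² to the Week 16 residual variance, so

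SE ratio ≈ √[1 + var(baseline) × (β₁₆ − b)² / R₁₆].

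For 32 versus 32, the SE with visit-specific slopes satisfies SE² = R₁₆ × (1/32 + 1/32) = R₁₆/16, so R₁₆ = 16 × SE².

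**Step 3: numbers.** Four simulated scenarios for 400 mg versus placebo, baseline mean 20, SD 8 (variance 64):

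| Noise, response | β₁₆ | b | SE, visit-specific | R₁₆ | Formula ratio | Simulated ratio |
|---|---|---|---|---|---|---|
| 25%, modest | −0.46 | −0.31 | 1.340 | 28.73 | √(1 + 64 × 0.15²/28.73) = 1.02 | 1.027 |
| 15%, modest | −0.47 | −0.15 | 1.204 | 23.19 | √(1 + 64 × 0.32²/23.19) = 1.13 | 1.131 |
| 10%, high | −0.61 | −0.12 | 1.082 | 18.73 | √(1 + 64 × 0.49²/18.73) = 1.35 | 1.347 |
| 5%, high | −0.61 | −0.04 | 1.055 | 17.81 | √(1 + 64 × 0.57²/17.81) = 1.47 | 1.465 |

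Formula and simulation agree. Over all simulated scenarios for PASI change the ratio ran from 1.02 to 1.47, and the common slope kept 4% to 71% of the Week 16 slope. Separate simulations with other assumed PASI inputs gave 2.5% to 23% (common slope keeping about 0% to 56%) and, with baseline SD 7 cut at 12, 3% to 21%. A formula-only grid reaches 2.00, but only by setting a slope of −0.8, baseline SD 10 and residual SD 5 together, without a response curve that produces them.

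**Step 4: bias.** In the 10%-noise, high-response row the mean estimates were −12.00 (common slope) and −11.90 (visit-specific). In the 15%-noise, modest-response row they were −9.31 and −9.30. There is no material average bias. Within a single trial, each 1-point baseline imbalance moves the Week 16 difference by 0.26 to 0.45 points relative to visit-specific adjustment. That is the same precision loss seen from another side, not an additional one.

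**Step 5: other cases.** Percent change: slope about 0 at every visit, ratio 1.00 (one scenario). PP-NRS: about 1%. Compound-symmetry fallback: 1.00 to 1.21 from slope misfit alone. PSI was not calculated.

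**The case against.** The strongest reply is that nothing decisive rests on this model. The primary endpoint is binary and analyzed without covariates. The main Week 16 PASI analysis is an ANCOVA with its own slope. Protocol 9.4.1 makes no multiplicity adjustment for the other continuous secondary endpoints, so they carry no confirmatory weight. This stands, and it is why the point is minor.

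Second, the size depends on inputs the documents do not give. A reader might infer that Week 16 is almost unadjusted for baseline. That happens only when early residual variance is small; elsewhere more than half of the adjustment can survive. Nor do the documents show that the slope climbs steadily to Week 16. Protocol 2.2.3 reports a placebo-adjusted PASI change of −14.02 at Week 4 for 400 mg, so much of the growth may come early. Fast onset does not remove the loss, however. With 75% of the effect reached by Week 4, the ratio was still 1.03 to 1.19, because Weeks 1 and 2 drive the common slope.

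Third, a reader might infer that any gap between ANCOVA and MMRM would be an artifact of the slope. The two differ by design: one imputes from control, the other uses observed data under missing at random. The slope is only an extra, avoidable source of difference.

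Fourth, one might extend the request to the longitudinal binary model in SAP 5.2.1, which has no baseline term. No calculation supports that, and in a logit model adding a covariate changes the odds ratio being estimated. It is not part of this point.

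**Conclusion.** The point holds as a minor one. As written, the MMRM imposes a single baseline slope on Weeks 1 to 16, and for absolute PASI change this under-adjusts the later visits. The loss is in precision: roughly 2% to 25% on the Week 16 standard error with baseline PASI mean about 20 and SD about 7, and up to 47% in the most extreme scenario simulated (SD 8, 5% noise, high response). All these figures assume complete data and inputs that the documents do not supply, so the direction is firmer than the size.

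The affected results are the supplementary Week 16 MMRM (6.2.3.2) and the MMRM of PASI change at other visits (6.2.4). A reader might infer that the main Week 16 PASI result or the primary conclusion is weakened. Neither is, because neither uses this model.

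**What to change.** In SAP 5.2.2, add the baseline-by-visit interaction to the fixed effects of the change-from-baseline MMRM. The model then has treatment, visit, treatment-by-visit, baseline and baseline-by-visit.

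The cost is one model term: seven slopes instead of one, so 7 − 1 = 6 degrees of freedom. No new data are needed. With complete data, every visit then has the same regressors and its own coefficients, so the Week 16 contrast equals the single-visit ANCOVA. Remaining differences between the two would then reflect their missing-data assumptions. In the 10%-noise, high-response scenario above, the standard error for 400 mg versus placebo falls from 1.46 to 1.08.

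Adding the MMRM program to the SAP appendices would remove any doubt about how baseline enters.
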